### 5.2 Inclusion criteria

- Present declaration of consent
- ECOG 0-2
- Ages 18-85
- Acinar adenocarcinoma of the prostate, histologically confirmed
- De novo oligo-/polymetastatic prostate cancer (min. 4 bone metastases) without Visceral and lymph node metastases are possible.
- First-line therapy with antihormonal therapy (AHT) + X (X = e.g., enzalutamide / abiraterone / apalutamide, etc.) according to urological guidelines as per S3 guideline for at least 6 months
- Present staging at the time of ED with multimetastasis, but exclusion of visceral metastases
- PSA not below the threshold of 0.2 ng/ml after 6 months of systemic therapy sunk
- ≥ 15 active osseous lesions in response assessment using PSMA-PET/CT after 6 months Systemic therapy

### 5.3 Exclusion criteria

- PSA after at least 6 months of systemic therapy < 0.2 ng/ml
- M1c (visceral metastases)
- other active tumor disease in the last 2 years (except basal cell carcinoma of the skin/melanoma in remission)
- Zn TUR-P or HIFU less than 6 months before RT start, Zn surgical resection of the prostate
- Pre-irradiation in the pelvic area
- Serious pre-existing conditions affecting the bladder or rectum (e.g., active fistula, chronic inflammatory bowel disease)
- Presence of a tumor predisposition syndrome
- serious pre-existing urological conditions
- Contraindications to performing a PSMA-PET/CT scan
- Contraindications to performing radiation therapy
- Pre-irradiation, which prevents ablative irradiation of the metastases
- In T4 stage: Persistent infiltration of the rectal mucosa after 6 months  
Systemic therapy; critical evaluation in case of bladder infiltration
- Rising PSA level: Indication to change systemic therapy or initiate a  
Chemotherapy before the start of the study

### 5.4 Necessary examinations and management prior to study enrollment:

- Histological confirmation of the tumor, preferably with Gleason score classification and indication of positive core needle biopsies (%); histological confirmation from a metastasis is possible, but not necessary.
- PSA level at the time of initial diagnosis and 6 months after initiation of combined therapy  
Systemic therapy at the time of study screening
- Imaging evidence of bone metastases at the time of initial diagnosis (preferably whole-body CT + whole-body bone scintigraphy, but at least one of the two examinations mentioned); optionally, a PSMA-PET/CT or PET/MRI may also have been performed at the time of initial diagnosis (if a PET/CT or PET/MRI was performed, a bone scintigraphy is not required)
- If any prior radiation therapy records exist, radiation therapy outside the pelvis should have been performed that is not related to the prostate cancer  
(Exception: radiation-induced gynecomastia prophylaxis during initiation of long-term ADT)
- Physical examination
- Documentation of the combined systemic therapy performed to date
- Contact and consultation with the primary treating urologist
- Tumor board decision
- Bone metastases that threaten structural stability, neurological deficits due to metastasis, stabilization of bone metastases by the introduction of metal

## 5.5 Patient discharge

Patients included in the study can withdraw from the study at any time at their own request and without giving reasons, and without affecting any future treatment or regular follow-up care after radiation therapy.

Exclusion from the study may occur at the discretion of the study physician for reasons of health risk (for example, if a serious comorbidity is present or if the planned radiation therapy is not possible due to prior radiation treatment). In the event of withdrawal from the study, the reason will be documented in the respective patient file and in the eCRF (CRF Drop-Out).

All patients who prematurely withdraw from the study after having already undergone a study intervention should receive a final examination immediately upon withdrawal, which should be documented in the eCRF (CRF Follow-Up). Furthermore, they should be offered a connection to the center as part of their regular radiotherapy follow-up care.

If consent to participate in the study is withdrawn, no further clinical data will be collected and no further study visits will be conducted. If a study intervention has already taken place, continued contact with the center for routine follow-up care after radiotherapy will be offered; no study data will be collected during this follow-up, only routine radiotherapy follow-up care will be provided. All data collected up to this point will be anonymized immediately, unless a request for complete data deletion is received. Treatment plans for treatments already administered within the study must be retained for 30 years in accordance with radiation protection regulations.

A cancellation of the planned study measures may become necessary for the following reasons:

- Disease progression necessitating the initiation of chemotherapy (e.g. Occurrence of visceral metastasis).
- Deterioration of general health, which precludes the continuation of the planned Measures prevented.
- An increase or doubling of the PSA level compared to baseline that is not attributable to a lesion requiring local therapy and necessitates a change in systemic therapy. If PSA progression according to Phoenix criteria is present, the next scheduled PSMA-PET scan is prioritized, and if isolated metastases are found, stereotactic radiotherapy is performed again. In cases of diffuse progression or the presence of visceral metastases, the therapy is adjusted according to the tumor board of the respective center.
- An increase in metabolically active lesions on PSMA imaging to a degree that prevents the implementation of local therapeutic measures.
- Acute toxicity CTCAE grade 4, showing no improvement.
- PSA doubling time < 6 months without imaging correlation.

If PSA levels rise during follow-up visits, the planned PSMA-PET/CT imaging for diagnostic purposes should be brought forward, and the study outpatient clinic should be consulted to determine whether newly occurring lesions should be treated with further local therapy.

## 5.6 Analysis of possible unforeseen severe side effects

An interim analysis to evaluate potential high-grade side effects 30 days after completion of radiation therapy is planned once a minimum of 9 patients have been enrolled (30 days after radiation therapy to the prostate and 30 days after radiation therapy to metastases). If there is a significantly increased number of CTCAE 3 adverse events (>25%), the course of the adverse events will be monitored after 90 days (assessment by two clinically experienced specialists from the study center); at this time, a resolution of acute post-radiation adverse events is expected. The study will continue if, 90 days after completion of radiation therapy, there is a significant improvement (to a maximum of CTCAE 2) in the acute adverse events in the majority of patients. If CTCAE 4 or CTCAE 5 toxicity occurs, patient recruitment will be stopped and a safety analysis will be conducted.

The study will only be resumed if a connection between the radiation therapy (SBRT of the prostate and metastases) and the toxicity that occurred can be ruled out.

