#### 4.3.3 Accompanying examinations:

**Planned measures:** These will take place at the time of study enrollment/before the start of radiation therapy, in parallel with radiation therapy, at the time of completion of radiation therapy and during the follow-up.  
Study visits.

**Implementation:** Follow-up visits are planned for the following times:

1. Pre-therapeutic for study inclusion and status assessment before the start of therapy (radiation of the prostate and metastases); six (up to a maximum of 9 months) after initiation of systemic therapy with evidence of a PSA value of  $>0.2$  ng/ml.
2. At the time of completion of therapy (radiation of the prostate and metastases).  
3rd month 1, 3, 6, 9, 12, 15, 18, 21 and 24 after study enrollment.

4. Subsequently, follow-up examinations are conducted as personal visits every 3 months to 18 months after completion of metastasis-directed therapy to record PSA levels, quality of life and to inquire about possible side effects.

**Specific burdens:** Attending study visits involves a time commitment, including travel to and from the study center and the visit itself, which lasts approximately 30-45 minutes. If the PSA level is checked in the patient's outpatient setting at the time of visits not related to the discussion of PSMA-PET findings, the questionnaires can be sent by mail. In this case, approximately 30 minutes should be allocated for completing the questionnaires per visit. The PSA level is checked via blood draw, which involves venipuncture. Theoretically, this procedure carries a risk of bleeding, infection, or tissue injury. However, blood draws with PSA level checks every 3 months are already part of routine urological therapy monitoring and are not an additional measure within the study.

**Benefit:** Regular study visits ensure close monitoring with consistent, frequent check-ups of PSA levels, a surrogate parameter for cancer progression. If PSA levels rise, appropriate diagnostic procedures can be initiated immediately, and any new findings can be investigated and treated. Medical consultations and assessments of quality of life allow for the initiation of appropriate therapy in cases of quality of life limitations or the occurrence of side effects. Furthermore, patients have reported that they appreciate and value a consistent connection to their treatment center.

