## 7. Clinical examinations (visits)

### 7.1 Overview of the accompanying investigations

The following CRF plan, Fig. 2, provides an overview of the accompanying investigations (study visits, PSA follow-up, QoL questionnaires, toxicity assessment, etc.):

	ADT + ARPI		PSMA-PET/CT	Therapie	Follow-Up												
Studienvisite	0	1		2	3	4	5	6	7	8	9	10	11	12	13	14	15
					1 Mo.	3 Mo.	6 Mo.	9 Mo.	12 Mo.	15 Mo.	18 Mo.	21 Mo.	24 Mo.	27 Mo.	30 Mo.	33 Mo.	36 Mo.
Intervention				SBRT Prostata			SBRT Met.										
Prüfung Ein- und Ausschlusskriterien		x															
Aufklärung und Einverständnis		x															
Registrierung		x															
Patientendatendokumentation		x															
Erhebung PSA-Wert	x	x			x	x	x	x	x	x	x	x	x	x	x	x	x
PSMA-PET/CT		x					x				x						
Dokumentation Lebensqualität		x		x	x	x	x	x	x	x	x	x	x	x	x	x	x
Dokumentation Nebenwirkungen				x	x	x	x	x	x	x	x	x	x	x	x	x	x

**Fig. 2:** Schedule of study-specific examinations. Study visits take place at the beginning of the radiation therapy, during the radiation therapy itself, and at the end of the radiation therapy.

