## 7.2 Study visits conducted

Specifically, the following parameters will be collected:

- 1) Examination at study enrollment: PSA level (current and trend), biopsies, staging examinations performed, and previously initiated systemic therapy. Assessment of baseline symptoms according to CTCAE v.5, EPIC, IPSS, and IIEF-5, as well as completion of the quality-of-life questionnaires (EORTC QLQ-C30, QLQ-PR25, and EQ-D5). Performance of a PSMA-PET/CT scan.
- 2) Weekly regular doctor consultations will be conducted concurrently with radiation therapy. At the start and end of radiation therapy, side effects will be assessed according to CTCAE v.5, EPIC-26, IPSS and IIEF-5, as well as quality of life (patient-reported: EORTC QLQ-C30 Prostate, QLQ-PR25, EQ-D5).
- 3) PSA levels should be monitored every 3 months via blood test until 30 months after completion of the last radiotherapy for metastases. This can be done at the center or in an outpatient setting, but due to potentially different underlying testing methods, it should preferably always be performed by the same provider, i.e., either at the center during the study visit or by the treating urologist/general practitioner.

In addition, quality of life (patient-reported: EORTC QLQ-C30 prostate, QLQ-PR25, EQ-D5) and possible side effects according to CTCAE v.5, EPIC-26, IPSS and IIEF-5 are recorded quarterly.

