#### 8.4 Interim evaluation

An interim evaluation of the study results is not planned. An analysis of the side effect profile will be conducted after one-third of the treated patients have been reached (see section 5.6).

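### The grade 3 safety review needs a CTCAE grade 30 days after metastasis radiotherapy, but no visit is scheduled there, so short-lived grade 3 events can be missed

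*Protocol*

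**What the plan says.** **The safety review.** Section 5.6 looks at high-grade side effects "30 days after radiation therapy to the prostate and 30 days after radiation therapy to metastases". It "is planned once a minimum of 9 patients have been enrolled"; section 8.4 places the same analysis "after one-third of the treated patients have been reached". If CTCAE grade 3 exceeds 25%, the events are followed to 90 days after RT. The study goes on if most patients have by then improved to grade 2 or lower.

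**The schedule.**
- Section 4.3.3 lists a visit at completion of therapy, then months 1, 3, "6, 9, 12, 15, 18, 21 and 24 after study enrollment", and then three-monthly personal visits until 18 months after metastasis-directed therapy. Where PSA is checked elsewhere and no PET result is to be discussed, it adds that "the questionnaires can be sent by mail".
- Section 7.2 takes CTCAE at the start and end of RT. For follow-up it says that "possible side effects according to CTCAE v.5, EPIC-26, IPSS and IIEF-5 are recorded quarterly".
- Fig. 2 (section 7.1) places stereotactic RT of metastases in the month 6 column. The next column is month 9.
- Section 4.3.2 puts metastasis RT six months after the first day of prostate RT.

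**The concern.** The review and the schedule were not written to the same clock. Section 5.6 counts from completion of each RT course and needs a reading at day 30. After metastasis RT the schedule offers a reading at the end of treatment and then nothing until about three months after month 6. A side effect that appears in the weeks after treatment and settles before month 9 falls between the two.

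The protocol presents the combination of prostate and metastasis RT as new in this setting. Section 5.6 is the only planned review of the grade 3 rate. A review that under-records events after the second course leans towards not triggering. A grade that was not taken at day 30 cannot be reliably reconstructed later.

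**Working it through.** **Size of the review and its trigger.** One third of the planned 27 patients is 27/3 = 9, which agrees with section 5.6. A rate above 25% of 9 means more than 0.25 × 9 = 2.25, so at least 3 patients.

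**Metastasis RT to the next visit.** Take a month as 30.44 days. Months 6 and 9 are then days 183 and 274, a gap of 91 days. Section 4.3.2 gives 3 to 5 stereotactic sessions, or up to 25 if normofractionated. I take these as about 1 to 2 weeks and 5 weeks (assuming five fractions a week for the long course). If RT starts at month 6:

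| Length of RT | Last fraction to month 9 |
|---|---|
| 1 week | 91 − 7 = 84 days |
| 2 weeks | 91 − 14 = 77 days |
| 5 weeks | 91 − 35 = 56 days |

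None is near day 30. Now count visits from enrollment, and assume 0 to 30 days from enrollment to prostate RT and 0 to 14 days of planning before metastasis RT. The range widens to 12 to 84 days. Some combinations then land near day 30 by accident. For example, a 14-day lag, 14 days of planning and 35 days of RT give 28 days. The following visit is then at about day 120, so day 90 is lost instead. If the three-monthly visits are counted from completion of metastasis therapy, the first is at about day 91, which serves day 90 and again leaves day 30 empty.

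**Prostate RT to month 1.** Section 4.3.2 gives 2 weeks for the ultrahypofractionated course and 4 weeks for the 20-fraction course. Counted from enrollment with no lag, month 1 falls 30 − 14 = 16 days or 30 − 28 = 2 days after the last fraction. With an assumed 14-day lag it falls 2 days after, or 12 days before, the last fraction. Counted from the end of prostate RT, it falls on day 30.

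**What incomplete recording does to the trigger.** This is an illustration only, because the protocol gives no expected grade 3 rate and no recording rate. Let X be binomial with n = 9 and probability p × c, where p is the true rate and c the share of events recorded. For p = 0.30:

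| Share recorded (c) | P(X ≥ 3) |
|---|---|
| 1.00 | 0.54 |
| 0.75 | 0.33 |
| 0.50 | 0.14 |

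**The case against.** The protocol has other safeguards, and they limit this point.

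- **A reader might infer that section 5.6 is the only safety gate.** It is not. The same section halts recruitment on grade 4 or 5 toxicity. Section 5.7 has RT paused and the study team told at once of any grade 3 or higher event. The synopsis has a separate stopping rule for persistent grade 3 events. The 25% trigger starts a 90-day follow-up; it does not itself stop the study.
- **A reader might infer that there is no baseline grade**, because the row "Dokumentation Nebenwirkungen" in Fig. 2 has no mark at visit 1. But section 7.2 requires "Assessment of baseline symptoms according to CTCAE v.5, EPIC, IPSS, and IIEF-5" at enrollment, CTCAE is taken again at the start of RT, and Fig. 2 marks visit 2. The missing mark is clerical.
- **A reader might infer that the 90-day recheck has no visit.** Month 9 falls 77 to 84 days after a 1- to 2-week course, which roughly serves it.
- **A reader might infer that mailed questionnaires replace clinician grading.** Section 4.3.3 lets questionnaires be mailed; it does not waive CTCAE. The text only leaves open how the grade is obtained at such visits.
- **Fig. 2 appears to run from prostate RT**, since months 1 and 3 stand after the therapy column. On that reading they approximate the 30- and 90-day prostate assessments.

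It is also fair to say that grading at the end of RT and weekly consultations during RT catch events under treatment, and that month 9 may pick up earlier events by recall. The immediate reporting in section 5.7 is worded around pausing RT, so it does not clearly reach events that begin after the last fraction. None of this supplies a scheduled reading 30 days after metastasis RT.

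**Conclusion.** The point holds in a limited form. Section 5.6 relies on a reading that sections 4.3.3 and 7.2 and Fig. 2 do not schedule. The first planned assessment after the end of metastasis RT is about 56 to 84 days later if RT starts at month 6 and lasts 1 to 5 weeks. Grade 3 events in that interval can be missed, not will be missed, and with a threshold of 3 in 9 the review can read low. How low depends on rates the protocol does not give.

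The inconsistent visit clock is a second, smaller defect. It leaves the 30-day prostate reading unsecured if section 4.3.3 is followed literally.

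Toxicity is an exploratory endpoint. The primary endpoint and the sample size of 27 are not affected. The study flowchart is illegible and the separate visit overview is not shown in the text available, so neither could be checked. Fig. 2 and the prose agree that nothing is scheduled 30 days after metastasis RT.

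**What to change.** In sections 4.3.3 and 7.2 and in Fig. 2, schedule the CTCAE assessments that section 5.6 uses at 30 and 90 days after the last fraction of each RT course:

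1. Add one clinician-graded contact 30 days after the last metastasis fraction. A telephone call suffices.
2. Anchor the month 1 and month 3 visits to the last prostate fraction, and the month 9 visit to the last metastasis fraction, so that they serve the other three points. For month 9 this means 90 − 84 = 6 to 90 − 56 = 34 days later than in the cases worked above.
3. State that the CTCAE grade at these four points is clinician-assessed even when questionnaires are mailed.
4. Add the missing side-effect mark at visit 1 in Fig. 2, to match section 7.2.

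The cost is wording in the protocol and CRF plus one short contact per patient, 27 in all. No procedure, threshold or stopping rule changes. It should be done before the first patient reaches metastasis RT, and preferably before enrollment.

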Aim of the Study	
Pilot study on radiological response after RECIP in PSMA-PET/CT in patients with primary metastatic prostate cancer Carcinoma, which occurs after 6 months in cases of oligopersistence
 
Systemic therapy administered as part of local ablative radiotherapy can be.
 
If the primary endpoint is reached, a multicenter study is planned, with an application for external funding (e.g., cancer support).

Objectives/Endpoints
 
 
• Primary Objective/Endpoint
 
• Secondary Objective/Endpoints
 
• Exploratory Objective
 
	
Primary endpoint: Response in PSMA-PET/CT after RECIP with a decrease in PSMA volume of at least 30%.
 
Secondary endpoints and parameters collected:
 
 
• PSA progression
 
• Lesion-specific response of the irradiated area Lesions on PSMA-PET/CT
 
• Objective response rate (ORR)
 
• Interval until change of systemic therapy
 
• Overall Survival (OS)
 
• Failure-free survival (FFS) as any disease-specific Event
 
• Progression-free survival (PFS)
 

	
 
Distant metastasis-free survival (MFS)
 
Disease-specific survival (prostate cancer specific survival, PCS)
 
 
Exploratory endpoints:
 
 
Reason for changing systemic therapy
 
Choice of the next systemic therapy line
 
Side effects (according to CTCAEV5 and RTOG), Quality of life (EORTC QLQ-C30 prostate, QLQ-PR25, EQ-D5), assessment of organ function (gastrointestinal and urogenital: IPSS score, ICIQ score, NCI-PRO-CTCAE, IIEF)
 

Statistics, Safety Variables and Stopping Rules	
Study design: Single-arm phase II study using the Fleming design
 
Number of cases: 27 patients
 
Statistical estimation: Significance level <math>p=0.05</math>; Null hypothesis: Success rate <math><15\%</math>, effectiveness of the intervention is certain if success rate <math>>40\%</math>, Power <math>90\%</math>.
 
Stopping rules: CTCAE grade 4 and 5 attributable to the therapy performed; persistent grade 3 adverse events <math>> 90</math> days after radiation therapy in <math>>50\%</math> of patients.

Database	
Database: REDCap
 
Biometrics: IKEaB, [name]

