The possible acute and long-term side effects correspond to the general side effects of radiation therapy to the pelvic region: pollakiuria, irritation of the bladder and/or urethra with irritation during urination. In the long term, a slight increase in urinary frequency and softer stool consistency may occur. Rarely, a slight deterioration in continence, more frequent urge to defecate with the occurrence of diarrhea or rectal mucus discharge may occur. In very rare cases, rectal bleeding, urinary retention with the possible need for the use of alpha-blockers with specific side effects or the need for indwelling catheterization, urethral stenosis, and, in extremely rare cases, the formation of a fistula or necrosis of the intestinal mucosa, requiring endoscopic or surgical intervention, may occur. The induction of a second malignancy cannot be ruled out (incidence of 1:100 to 1:1000 after 10 to 30 years), however, this already low risk is negligible in light of the polymetastatic prostate cancer disease.

**Specific burdens of metastasis radiotherapy:** Radiotherapy of metastases is associated with additional time commitment for appointments (3-5 for stereotactic radiotherapy; up to 25 for normofractionated radiotherapy). Depending on the number of metastases being treated, the duration of each radiotherapy session can be up to one hour. Depending on the location of the metastases, corresponding side effects from the radiotherapy may occur; however, the normal tissue constraints are chosen so that the risk of long-term side effects is 1-2%, and the focus is on maximum sparing of normal tissue. Furthermore, only metabolically active and therefore therapy-resistant metastases are treated, where further growth and thus potential complications due to local progression would be expected if no local radiotherapy or a change in systemic therapy were performed.

**Benefit of the therapy (radiation of the prostate and metastases):** The planned short-term ablative radiation therapy of metabolically active lesions, with a favorable side effect profile, aims to eliminate system therapy-resistant tumor cells in oligoresidual disease with a poor oncological prognosis. It is assumed that resistance to system therapy is driven by these resistant tumor cells. The targeted elimination of these therapy-resistant tumor cells should delay the development of resistance to system therapy, thereby extending progression-free survival and ultimately overall survival.

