#### 4.4 Sample Size Estimation and Recruitment Period Based on existing

publications regarding PSA response to complete androgen blockade and irradiation of bone metastases, a radiological response after RECIP with a PSMA volume reduction of at least 30% is expected to be achieved in 40% of patients through the study intervention. If the success rate remains below 15%, it is assumed that the therapy provides no benefit. The study hypothesis will be rejected with a sample size of 27 patients (power of 90%, one-sided significance level  $\alpha=0.05$ ) if  $>5/27$  patients do not show a response after RECIP 12 months following metastasis-directed therapy.

At the urological center in Tübingen, approximately one patient per week with a new diagnosis of primary bone metastases in prostate cancer is presented to the tumor board. Considering the expected inadequate treatment response in approximately 20-30% of cases and adhering to the inclusion and exclusion criteria, a realistic number of 5-10 patients per center could be enrolled within one year. Therefore, a recruitment period of 12 months was chosen for the target of 6 centers.

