## 5.7 Interruption and termination of the study

If a grade 3 or higher adverse event occurs, radiation therapy will be paused and appropriate supportive care initiated. The study team will be informed immediately, and the principal investigator will be consulted regarding the possible continuation of radiation therapy.

Should a grade 4 toxicity occur during treatment within the study, irrespective of the planned interim analysis regarding adverse events, and which cannot be controlled with supportive measures, then the study intervention must be interrupted until the observed toxicity subsides. The toxicity must be documented as a serious adverse event (SAE). The principal investigator is entitled to terminate the clinical trial prematurely for relevant medical/administrative reasons if

- Serious, irreversible adverse events (toxicity grade 4 or 5) occur that are clearly related to the study intervention under investigation (i.e., radiation of the prostate and metastases).
- the targeted patient recruitment does not take place within a reasonable timeframe • the research question under investigation becomes obsolete during the study due to new scientific findings and no longer serves the scientific purpose  
should meet the standard
- serious data quality problems should occur that cannot be resolved  
can
- unforeseen circumstances arise at the individual center that prevent the continuation of the  
Do not allow clinical trial
- in the event of relevant and serious violations of the study protocol
- Compliance with legal or ethical regulations cannot be guaranteed  
can.

The reasons for discontinuing the study will be documented in detail. Patients still undergoing treatment at the time of discontinuation will receive a final examination, which will be documented in the eCRF. If a study physician raises ethical concerns regarding the continuation of the study, these concerns must be reported to the principal investigator immediately. The principal investigator, in consultation with the co-principals, will decide on the discontinuation of the study.

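### The toxicity stopping provisions in the synopsis, 5.6 and 5.7 do not agree, and at planned accrual the metastasis part of the 9-patient look comes when recruitment is nearly or fully complete

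*Protocol*

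**What the plan says.** **Synopsis, stopping rules.** The study stops for "CTCAE grade 4 and 5 attributable to the therapy performed; persistent grade 3 adverse events" lasting beyond 90 days after radiotherapy in more than 50% of patients.

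**Section 5.6.** A side-effect analysis "is planned once a minimum of 9 patients have been enrolled", covering 30 days after prostate irradiation and 30 days after metastasis irradiation. Section 8.4 places it at one-third of treated patients. If grade 3 events exceed 25%, their course is checked at 90 days: "The study will continue if, 90 days after completion of radiation therapy, there is a significant improvement (to a maximum of CTCAE 2") in the majority of patients. For higher grades: "If CTCAE 4 or CTCAE 5 toxicity occurs, patient recruitment will be stopped and a safety analysis will be conducted". The study resumes only if a link between the radiotherapy and the toxicity can be excluded.

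**Section 5.7.** Regardless of that analysis, a grade 4 toxicity that supportive care cannot control interrupts the study intervention until it subsides. The principal investigator is entitled, but not obliged, to end the trial if "Serious, irreversible adverse events (toxicity grade 4 or 5) occur that are clearly related to the study intervention".

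**Timing.** Metastasis irradiation begins six months after the first day of prostate irradiation (4.3.2). Recruitment is to take 12 months (4.4), from 12/2025 to 12/2026 (synopsis).

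**The concern.** A stopping rule has to give one answer for one set of data, wherever in the protocol the investigator looks it up. Here the three places use different attribution standards, different conditions for restarting, and a percentage with no stated denominator. Several centres are planned, so two sites could read the same event differently and each be following the protocol.

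The timing raises a second question. The action that 5.6 names for severe toxicity is a stop to recruitment. Metastasis irradiation comes half a year after entry, so a look at its toxicity may arrive when few or no patients remain to be recruited. Nothing in 5.6 says what the look would then decide.

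**Working it through.** **1. The plan's own figures.** Section 4.4 gives "power of 90%, one-sided significance level" 0.05, a null rate of 15% and a target rate of 40%. With 27 patients and success declared at 8 or more responders, the exact binomial gives P(X ≥ 8 | 0.15) = 0.0398 and P(X ≥ 8 | 0.40) = 0.905. So 27 is reproduced, and 27/3 = 9 agrees with 8.4.

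**2. Grade 4, passages side by side.** Take one grade 4 event that is related to radiotherapy and resolves.

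| Place | Condition | Consequence |
|---|---|---|
| Synopsis | attributable grade 4 or 5 | listed as a stopping rule |
| 5.6 | any grade 4 or 5 | recruitment stops; resumption only if a link is excluded, which a related event cannot satisfy |
| 5.7, interruption | uncontrolled grade 4 | intervention interrupted until the event subsides |
| 5.7, termination | irreversible and clearly related | discretionary; a reversible event does not qualify |

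The same event is a stop, a recruitment halt with no exit, or at most a temporary interruption. This needs no numerical assumption.

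**3. Grade 3, the denominator.** More than 25% of 9 means at least 3 patients (2/9 = 22%, 3/9 = 33%). Suppose 3 are affected and 2 still have grade 3 at 90 days.

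- Counting affected patients: 2/3 = 67% persist and 1/3 improved. The synopsis stops and 5.6 does not permit continuation.
- Counting all patients: 2/9 = 22% persist and 7/9 are at grade 2 or below. The synopsis does not stop and 5.6 permits continuation.

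On either common count the two rules agree, and they part only at exactly 50%. The defect is that neither place says which count applies.

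To show how much this matters, **assume** a true rate p of persistent grade 3 and no transient grade 3. On affected patients the study is blocked once 3 of 9 have an event, since none improves. On all patients the synopsis needs 5 of 9, or 14 of 27 if the full sample is meant.

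| Assumed p | P(≥3 of 9) | P(≥5 of 9) | P(≥14 of 27) |
|---|---|---|---|
| 0.10 | 0.053 | 0.001 | <0.001 |
| 0.20 | 0.262 | 0.020 | <0.001 |
| 0.30 | 0.537 | 0.099 | 0.014 |
| 0.40 | 0.768 | 0.267 | 0.145 |
| 0.50 | 0.910 | 0.500 | 0.500 |

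The protocol gives no expected rate for persistent grade 3, so p is illustrative. Transient events would change the first column.

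**4. Timing of the look.** Inputs: 27 patients in 12 months, taken as uniform, is 27/12 = 2.25 per month, so patient 9 enters at 9/2.25 = month 4.0. Planning takes up to 10 working days (4.3.2), about 0.5 month. Metastasis irradiation runs from 3–5 sessions to 25 (4.3.2). I allow 0 to 1 month for planning and 0 to 1.25 months for treatment.

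Look = 4.0 + planning + 6 + treatment + 1; enrolled = min(27, 2.25 × month).

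| Planning | Treatment | 30-day look (month) | Enrolled | 90-day check (month) |
|---|---|---|---|---|
| 0 | 0 | 11.0 | 24.75 | 13.0 |
| 0.5 | 0.25 | 11.75 | 26.4 | 13.75 |
| 0.75 | 0.5 | 12.25 | 27 | 14.25 |
| 1 | 1.25 | 13.25 | 27 | 15.25 |

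The 90-day check always falls after month 12. At the rate in 4.4 (6 centres, 5 to 10 patients each per year), 26.5 to 27 are enrolled at the 30-day look.

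The prostate part differs: 4.0 + planning (0 to 0.75) + treatment (0.25 to 1) + 1 = month 5.25 to 6.75, with about 12 to 15 enrolled.

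**The case against.** **Grade 3.** A reader might infer that the synopsis and 5.6 flatly contradict each other on grade 3. The text does not support that. Both use day 90, a majority and the word patients, and a conflict appears only if one is read on affected patients and the other on all. The 25% figure is the entry to the 90-day check, not a rival stopping rule. What stands is an undefined denominator.

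**Grade 4/5.** Section 5.6 can be read as pause, assess, then attribute, which is close to the synopsis; and 5.7 partly concerns other actions, for which other thresholds are legitimate. This is fair for unrelated events. It does not settle the related, reversible event. Reading the 5.7 interruption as applying to one patient does not settle it either: the text speaks of the study intervention and does not mention the recruitment stop or its resumption condition.

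**Timing.** It would be too strong to say that the look cannot act on recruitment. The lower bound is about 25 of 27, and the figure assumes accrual on schedule. Only one external collaboration exists so far (4.5). With two centres at 5 to 10 patients a year, about 15 to 24 would be enrolled at the 30-day look, but accrual would then overrun the planned 12 months. Slow opening within those 12 months moves the look later.

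Nor is the look the only safeguard. The grade 4/5 recruitment stop in 5.6 and the radiotherapy pause at grade 3 or above in 5.7 carry no patient-number condition.

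**Expected risk.** A reader might set the assumed rates above against the statement in 4.3.2 that "the normal tissue constraints are chosen so that the risk of long-term side effects is 1-2"%. That sentence concerns metastasis irradiation and long-term effects in general, so it is not a benchmark for persistent grade 3 after both treatments.

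**Conclusion.** The point holds in three parts of different strength.

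- **Grade 4, related and reversible:** inconsistent on the text alone, with no assumption needed. This carries the most weight.
- **Grade 3:** undefined rather than contradictory. The choice of denominator reverses the decision at 3 of 9 affected with 2 persisting. At an assumed 30% persistent rate without transient events, it moves the chance of stopping at nine patients from 0.10 to 0.54.
- **Metastasis look:** at planned, uniform accrual it falls at about month 11 to 13 with about 25 to 27 of 27 enrolled, and the 90-day check falls after recruitment closes. This part can hardly act through recruitment. Slower accrual weakens the point, and the prostate part is not affected.

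The late look is not useless: by month 11 to 13 roughly half the patients would not yet have started metastasis irradiation. The gap is that 5.6 does not say what the look decides at that stage. Because the rules concern severe toxicity, they should be settled before enrolment starts.

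**What to change.** 1. Reconcile the synopsis, 5.6 and 5.7 into one set of rules, cross-referenced rather than restated, with one stated denominator, one attribution standard and one resumption condition. Say which provisions apply to a single patient's treatment and which to the study.
2. Tabulate the probability of stopping under the reconciled rule over a range of toxicity rates, each labelled as an assumption.
3. State the prostate and metastasis looks as two separately dated reviews. Have the investigators state what decision the metastasis look governs, given that recruitment will be nearly or fully complete by then.

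The clinical thresholds and actions are for the investigators to set. The cost is a protocol amendment in wording, one small table, and one additional summary of data already collected. The sample size does not change.
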